1.2 Rationale

ApoPharma Inc. is currently conducting an 18-month trial, TIRCON2012V1, to assess the safety and efficacy of deferiprone in patients with PKAN. In that study, a planned 90 participants are being randomized in a 2:1 ratio to receive either deferiprone oral solution or placebo. Patients are scheduled to undergo weekly monitoring of absolute neutrophil count (ANC) and to undergo safety and efficacy assessments at Months 1.5, 3, 6, 12, and 18.

Patients who complete TIRCON2012V1 will be invited to enroll in the current study, in which all participants will receive deferiprone. Participants will thus receive deferiprone for a total of either 1.5 years or 3 years, depending on which treatment was assigned in the earlier study. The long-term data obtained will enable a better understanding of the use of deferiprone in this patient population.

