3 STUDY DESIGN

3.1 Description of Study Design

Study TIRCON2012V1-EXT is an 18-month, multi-center, single-arm, open-label extension of study TIRCON2012V1, which began in 2012 and is currently in progress. In the initial study, patients with a diagnosis of PKAN are being randomized in a 2:1 ratio to receive 18 months of treatment with either deferiprone or placebo, respectively. All participants who complete TIRCON2012V1 will be offered the opportunity to continue in the extension study, with the final visit of the initial study being considered Visit 1 of the extension study. (The 4-week follow-up visit that is planned at the end of study TIRCON2012V1 will be cancelled for individuals who choose to continue.) Patients who had been randomized to

receive deferiprone in study TIRCON2012V1 will continue to receive deferiprone in the extension study, while those who had been randomized to receive placebo will be switched to deferiprone. Since the initial study will still be in progress at the time that the first patients enter the extension study, patients and study staff will remain blinded until the initial study is over as to which product was received for the previous 18 months.

Patients will have their hematology blood counts monitored weekly, and will return to the study site at 6 months (Visit 2), 12 months (Visit 3), and 18 months (Visit 4) for assessments of safety and efficacy. Due to the difficulties that travel may pose for patients with PKAN, participants will have the option of arranging for the Visit 2 and Visit 3 assessments to be done locally instead. Details are provided in [Section 5.1](#).

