extension study. Continuous variables will be compared by paired t-tests while proportions by McNemar's test. If statistically significant imbalances are detected, they will be adjusted accordingly for the comparison of changes in BAD and PGI-I between the initial study and the extension study by using a MMRM model approach that is consistent with the analysis of these two efficacy measures in the initial study. The MMRM model is specified below.

The MMRM model will be applied to non-imputed data from the observed cases (OC) data set. Let y_i denote the vector of n_i continuous post-baseline measurements observed for study patient i . Each response (i.e., each element of y_i) will be defined as the patient's score at that occasion minus the baseline score.

The model will assume that the distribution of y_i is multivariate normal,

$$y_i \sim N(X_i\beta, \Sigma_i),$$

where X_i is a design matrix of dimensions $n_i \times p$, β is a vector of coefficients of length p , and Σ_i is an $n_i \times n_i$ covariance matrix.

The MMRM model will include baseline value of the outcome as a covariate and treatment group as the main factor in the model. A change in DBS settings or use of medications that have the potential to affect dystonia symptoms during the study may confound the treatment effect assessment (named outcome impacting medication use hereafter) for DFP vs. placebo between the initial study and the extension study for patients who were on placebo in the initial study. Hence, both variables will also be included in the MMRM model as visit-dependent covariates.

The visit-dependent covariate for DBS settings change is defined as follows: for patients with DBS at enrollment, if there is any DBS setting change since the previous visit, it will be coded as 'DBS Setting Change' for the current visit or 'No DBS Setting Change' otherwise. For example, if a patient has a DBS setting change between the outcome assessment dates at month 6 visit and month 12 visit, it will be coded as 'DBS Setting Change' for month 12 visit in the model. For those patients without DBS at enrollment, it will be coded as 'No DBS'. A discrete variable, DBSCHG, with three categories will be included in the MMRM model.

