The visit-dependent covariate for the outcome impacting medication use will be defined according to whether the patient is on a regular dosing regimen or on a PRN (as needed) dosing regimen between two visits. For patients treated on a regular dosing regimen, if there is a dose change or starting of new medication since the previous visit, it will be coded as 'Yes' for the current visit and the future follow-up visits or 'No' otherwise in the model. For patients who do not use any outcome impacting medication, it will be coded as 'No'.

For patients on a PRN (as needed) dosing regimen, the visit-dependent covariate will be defined according to the treatment impact period in the following table.

Medication	Treatment impact period
Baclofen	30 days
Trihexyphenidyl	30 days
Clonazepam	30 days
Tizanidine	30 days
Botox	60 days
Tetrabenazine	90 days

If the PRN drug is started within the treatment impact period prior to the assessment date of an outcome for a visit, it will be coded as ‘Yes’ for that visit. If the drug is started outside this time window but is not interrupted within this period, it will also be coded as ‘Yes’ for that visit. Under other conditions, it will be coded as ‘No’ in the model. A binary variable for the outcome impacting medication use, RESMED, will be included in the MMRM model.

The frequency of PRN drug or rescue medication use between two outcome assessment dates of current visit and the previous visit will also be included in the MMRM model as a quantitative visit-dependent covariate, NDRUG, for the current visit.

The MIXED procedure in SAS will be used for the MMRM model analysis. Data within each patient at different visits will be considered repeated measures. AR(1) (autoregressive of order 1) covariance structure will be used to model the correlation between repeated measures within the same patient and Kenward and Roger’s method will be used to estimate the denominator degrees of freedom. The 95% confidence interval (CI) for the difference between the two treatments will be calculated by the LSMEANS statement.

A sample SAS code for the MMRM model is presented in the box below:

```
proc mixed;
  class TREAT USUBJID VISIT DBSCHG RESMED;
  model CHG=TREAT VISIT TREAT*VISIT BASE DBSCHG RESMED
  NDRUG/solution ddfm=kr;
  repeated VISIT/ subject=USUBJID type=ar(1);
  lsmeans TREAT*VISIT / diff cl;
run;
```

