where TREAT is the indicator variable for treatment group (DFP vs. Placebo), USUBJID represents the patient ID, VISIT is the discrete variable representing the scheduled study visit after the baseline visit, DBSCHG is the discrete variable with three categories for

DBS settings change (DBS Setting Change, No DBS Setting Change, No DBS), RESMED is the binary variable for outcome impacting medication use (Yes vs. No), CHG is the change in value of efficacy outcome from baseline to the scheduled visit, BASE is the baseline value of efficacy outcome, and NDRUG is the frequency of PRN drug or rescue medication use.

PGI-I is already a measurement of change from baseline and thus will be used directly as the outcome variable and baseline BAD score will be included as the baseline value in all models.

McNemar's test will be used to compare the proportion of responders in the initial study with the proportion of responders in the extension study.

For all patients who were on DFP in both studies, the longitudinal response profile for BAD score will be explored by a MMRM model with time modelled as a continuous variable.

For this model, AR(1) (autoregressive of order 1) covariance structure will be used to model the correlation between repeated measures within the same patient and Kenward and Roger's method will be used to estimate the denominator degrees of freedom.

A sample SAS code for this MMRM model is presented in the box below:

```
proc mixed;  
  class USUBJID VISIT;  
  model BAD= TIME /solution ddfm=kr;  
  repeated VISIT/ subject=USUBJID type=ar(1);  
run;
```

where USUBJID represents the patient ID, VISIT is the discrete variable representing the scheduled study visit after the baseline visit, BAD is the value of BAD score at each time point, and TIME is the time in months at each time point corresponding to each visit.

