	Month 12	xx xx.xx (xx.x) xx.x (xx.x, xx.x) 0.xxxx	xx xx.xx (xx.x) xx.x (xx.x, xx.x) 0.xxxx	0.xxxx
	Month 18	xx xx.xx (xx.x) xx.x (xx.x, xx.x) 0.xxxx	xx xx.xx (xx.x) xx.x (xx.x, xx.x) 0.xxxx	0.xxxx
Repeat for other body regions	

§ Paired T-test

Table 14.2.2.5 Proportions of responders in BAD total score at each follow-up visit for patients on placebo in initial study – ITT population

	Visit	Placebo in TIRCON (N=xx)	DFP in TIRCON-EXT (N=xx)	DFP Vs. Placebo p -value [§]
Responder in BAD total score n (%)	Month 6	xx (xx.x)	xx (xx.x)	0.xxxx
	Month 12	xx (xx.x)	xx (xx.x)	0.xxxx
	Month 18	xx (xx.x)	xx (xx.x)	0.xxxx

§ McNemar's test

Similar Table 14.2.2.5a will be based on PP population

Table 14.2.2.6 PGI-I score at each follow-up visit for patients on placebo in initial study – ITT population

	Visit	Placebo in TIRCON (N=xx)	DFP in TIRCON- EXT (N=xx)	DFP Vs. Placebo p -value [§]
PGI-I n Mean (SD) Median (Min, Max) p -value [§]	Month 6	xx xx.xx (xx.x) xx.x (xx.x, xx.x) 0.xxxx	xx xx.xx (xx.x) xx.x (xx.x, xx.x) 0.xxxx	0.xxxx
	Month 12	xx xx.xx (xx.x) xx.x (xx.x, xx.x) 0.xxxx	xx xx.xx (xx.x) xx.x (xx.x, xx.x) 0.xxxx	0.xxxx
	Month 18	xx xx.xx (xx.x) xx.x (xx.x, xx.x) 0.xxxx	xx xx.xx (xx.x) xx.x (xx.x, xx.x) 0.xxxx	0.xxxx

§ Paired T-test

Similar Table 14.2.2.6a will be based on PP population

Table 14.2.2.7 Proportions of responders in PGI-I at each follow-up visit for patients on placebo in initial study – ITT population

	Visit	Placebo in TIRCON (N=xx)	DFP in TIRCON-EXT (N=xx)	DFP Vs. Placebo p -value [§]
Responder in PGI-I n (%)	Month 6	xx (xx.x)	xx (xx.x)	0.xxxx
	Month 12	xx (xx.x)	xx (xx.x)	0.xxxx
	Month 18	xx (xx.x)	xx (xx.x)	0.xxxx

§ McNemar's test

Similar Table 14.2.2.7a will be based on PP population

Table 14.2.2.8 Summary of DBS settings change and medication use with a potential outcome impact for patients on placebo in initial study – ITT population

Visit		Group	
		Placebo in TIRCON (N=xx)	DFP in TIRCON-EXT (N=xx)
Month 6	DBS Settings: n (%)		
	DBS Setting Change	xx (xx)	xx (xx)
	No DBS Setting Change	xx (xx)	xx (xx)
	No DBS	xx (xx)	xx (xx)
	Outcome Impacting Medication Use: n (%)		
	Yes	xx (xx)	xx (xx)
No	xx (xx)	xx (xx)	
	Frequency of PRN drug or rescue medication use (Mean ± SD)	xx ± xx.x	xx ± xx.x
	Median	xx	xx
	(Minimum, Maximum)	(xx, xx)	(xx, xx)
Repeat for other visits
Overall

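### The PRN/rescue medication frequency has no time denominator, so shorter follow-up on deferiprone can create or hide an imbalance in the test that selects the model for the former-placebo comparison

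*SAP*

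**What the plan says.** SAP section 4 introduces the covariate: "The frequency of PRN drug or rescue medication use between two outcome assessment dates of current visit and the previous visit will" be a quantitative, visit-dependent term in the MMRM. The note to the SAS code repeats that "NDRUG is the frequency of PRN drug or rescue medication use". The model statement has no offset or interval-length term.

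The same section compares PRN/rescue frequency between the initial study and the extension for patients first randomised to placebo: "Continuous variables will be compared by paired t-tests while proportions by McNemar's test". It does not say whether that test is made visit by visit or on the whole period. The shell of Table 14.2.2.8 has rows by visit and an overall row. It uses whole-number placeholders for the median and range, and has no exposure row and no p-value column.

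SAP section 3.5 attaches a consequence. With a significant imbalance, the comparison uses the MMRM on observed cases; otherwise it uses a paired t-test on last observed data. Protocol section 9.4.1.3 sets up the same conditional adjustment and leaves the model to the SAP.

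**The concern.** A count depends on how long the patient was watched. The two periods of one patient are not guaranteed the same length, and the asymmetry runs one way. Completion of the initial study is an inclusion criterion (Protocol section 4.2), so each former-placebo patient has a full placebo period of about 18 months. Only the deferiprone period can be shortened. A patient who leaves the extension early but has one post-baseline efficacy assessment stays in the ITT population (SAP section 3.3), so short deferiprone periods enter the paired test.

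The test result decides both the model and the missing-data handling for a secondary comparison. If it partly reflects follow-up length, that choice is partly arbitrary. A real rise in use on deferiprone could also be offset by truncation and pass unnoticed.

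**Working it through.** **Plan's own figure.** There is none to reproduce. SAP section 3.2 states that no sample size or power calculation was made, and neither document gives a PRN/rescue use rate.

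**Inputs from the documents.**
- Pairs: 24 former-placebo patients (SAP section 3.2; 44 + 24 = 68).
- Two-sided significance level: 0.05 (SAP section 3.6).
- Period length: 18 months each.
- Proxy for extension drop-out: initial-study non-completion, 89 − 76 = 13, and 13/89 = 14.6% (SAP section 3.2).

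**Assumptions.**
- Use rate from 1 per 18 months to 2 per month, identical in both periods.
- Counts Poisson, or gamma-Poisson with between-patient shape 1 or 0.5.
- Drop-out of 10%, 14.6% or 25%, at a time uniform between month 1 and month 18 (mean 9.5).

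**Expected shift in the count.** Mean observed deferiprone months = 18 − d × (18 − 9.5), where d is the drop-out proportion.
- d = 0.10: 18 − 0.85 = 17.15; 17.15/18 = 0.953
- d = 0.146: 18 − 1.24 = 16.76; 16.76/18 = 0.931
- d = 0.25: 18 − 2.125 = 15.88; 15.88/18 = 0.882

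With equal rates, the mean deferiprone count is therefore about 5%, 7% or 12% too low. Conversely, a true rate on deferiprone higher by a factor of 1/0.953 = 1.05, 1/0.931 = 1.07 or 1/0.882 = 1.13 gives equal expected counts and is masked.

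**False-imbalance rate.** For 24 differences (deferiprone count minus placebo count), t = mean/(SD/√24) on 23 degrees of freedom, with 20,000 replicates per setting. The table shows per cent of trials with p < 0.05; ranges run over the three dispersion settings.

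| Use rate | No drop-out | 10% | 14.6% | 25% |
|---|---|---|---|---|
| 1 per 18 months | 4.4–5.2 | 4.9–5.1 | 5.0–5.6 | 5.7–7.2 |
| 0.25 per month | 4.6–5.0 | 4.9–6.0 | 5.5–7.7 | 8.6–12.7 |
| 1 per month | 4.4–5.1 | 5.1–8.6 | 6.5–12.2 | 11.5–25.9 |
| 2 per month | 4.3–5.1 | 5.1–9.9 | 6.8–16.1 | 13.5–35.9 |

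With uses divided by months observed, the rate is 4.1–5.1% in every drop-out setting. A second simulation of the truncation effect gave about 5–13% at 14.6% drop-out and 6–26% at 25%, within the ranges above.

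**If the test is per visit.** The table concerns a whole-period count. A per-visit count is affected through irregular intervals. A termination assessment at month 10 falls in the Month 12 window (9 to <15 months), with a look-back of 10 − 6 = 4 months instead of 6. If Month 12 is missed, the Month 18 look-back is 18 − 6 = 12 months.

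**The case against.** *The SAP never says count.* True: it says frequency, which could mean a rate. But the variable name, the whole-number placeholders and the missing exposure row point to a count. Where the SAP wants a rate, as for adverse events per 100 patient-years (section 4.4.1), it says so.

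*The effect is small.* This largely stands. At 14.6% drop-out the upper figures need frequent use, whereas the protocol restricts PRN and rescue use and has the sponsor notified after more than 2 rescue events (section 4.7). At one use per 18 months, the test stays near 5%.

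*The treatment estimate is not harmed.* This stands as far as it was checked. Table 14.2.2.9 reports Visit 4. A least-squares check with a 3- versus 6-month Month 6 look-back, equal rates, no treatment effect and no drop-out gave a Visit 4 bias within about 0.015 BAD points, which is Monte Carlo error. What remains is the effect on model selection.

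*A reader might infer something much worse.* Protocol section 1.2 gives the initial study "safety and efficacy assessments at Months 1.5, 3, 6, 12, and 18", while the extension has only Months 0, 6, 12 and 18. If Month 3 were the visit before Month 6, the placebo look-back would be 3 months against 6 on deferiprone. With equal rates, a Month 6 test would then be falsely significant in 15–20% of trials at one use per 18 months and 52–65% at 0.25 per month. The documents do not support this as the intended reading. The SAP's efficacy windows start at Month 6, its Month 1.5 and 3 windows are for safety data only, and the former-placebo tables list only Months 6, 12 and 18 after baseline. A Month 3 assessment at or just after 3 months would fall inside the Month 6 window and be averaged into it. Nor is a separate Month 6 imbalance test specified. A 15- versus 18-month total would need Month 3 to start the look-back while its own interval was discarded. Still, the SAP does not name the visit before Month 6, so the reading is not expressly excluded.

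**Conclusion.** The point holds in a limited form. The frequency has no time denominator, only the deferiprone period can be shortened by early termination, and the resulting test selects the analysis. With equal true rates, false imbalance is about 5–16% at 14.6% drop-out and up to 36% at 25% drop-out with very frequent use. When the two periods are equal in length it is 4–5%. These figures rest on assumed use rates, an extension drop-out rate borrowed from the initial study, and a whole-period count as the tested quantity.

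The documents do not establish a built-in 3- versus 6-month artefact, and bias in the Visit 4 estimate has not been shown. The comparison is secondary, in an extension whose primary objective is safety. The change is worth making because it is nearly free and removes a dependence on follow-up length.

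**What to change.** Amend SAP section 4 and Table 14.2.2.8 before the analysis:
- In the imbalance test, compare total PRN/rescue uses divided by months observed in each study period, and state that the test is on the whole period.
- Define NDRUG as uses per month since the previous Month 0/6/12/18 assessment of the same period, dividing by the actual interval so that early-termination and missed visits are handled.
- State that the visit before Month 6 is baseline in both studies, and that the initial study's Month 1.5 and Month 3 visits do not start a look-back.
- Add months observed to Table 14.2.2.8.

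The cost is a few lines of SAP text and one division in the derivation. Medication start and stop dates are already recorded (Protocol section 7.2.3.4), and assessment dates are already needed for the visit windows. No new data are required.

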3.1 Study Design

Study TIRCON2012V1-EXT is an 18-month, multi-center, single-arm, open-label extension of study TIRCON2012V1. In the initial study, patients with a diagnosis of PKAN were being randomized in a 2:1 ratio to receive 18 months of treatment with either deferiprone or placebo, respectively. All participants who completed TIRCON2012V1 were offered the opportunity to continue in the extension study, with the final visit of the initial study being considered Visit 1 of the extension study. Patients who had been randomized to receive deferiprone in study TIRCON2012V1 continued to receive deferiprone in the extension study, while those who had been randomized to receive placebo were switched to deferiprone. Since the initial study were still in progress at the time that the first patients entered the extension study, patients and study staff remained blinded until the initial study was over as to which product was received for the previous 18 months.

In the TIRCON-EXT study, patients will have their hematology blood counts monitored weekly, and will return to the study site at 6 months (Visit 2), 12 months (Visit 3), and 18 months (Visit 4) for assessments of safety and efficacy.

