3.2 Determination of Sample Size and Study Power

There was no formal sample size and power calculation for this study. All patients who completed TIRCON2012V1 study were invited to enroll in the extension study. Among the 89 subjects randomized in TIRCON2012V1 study, 76 completed the study and 68 subjects were subsequently enrolled in this extension study (44 originally randomized to the deferiprone group and 24 in the placebo group).

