3.6 Statistical Software and Level of Significance

All statistical analyses will be performed using SAS (version 9.3 or higher) on Windows operating system. Null hypotheses tested are that there are no differences in true parameter between comparison groups, unless otherwise stated. A two-sided *p*-value of 0.05 will be used as the significance level for the determination of statistical significance in all statistical tests.

4 Statistical Analyses

The efficacy endpoints are defined as follows:

All patients:

- Change in the BAD total score from baseline (defined as prior to the start of deferiprone therapy) to Visit 4, as assessed by central evaluation of videotapes
- Proportion of patients with improved or unchanged BAD scale total score between baseline and Visit 4 (responder analysis, responders defined as change in BAD total score to be ≤ 0)
- Change from baseline to Visit 4 in BAD scale score per body region (eyes, mouth, neck, trunk, and each upper and lower extremity), as assessed by central evaluation of videotapes
- PGI-I score at Visit 4
- Proportion of patients showing an improvement on PGI-I at Visit 4 (responder analysis, responders are defined as patients whose conditions have not deteriorated; patients who have “no change”, or are “minimally improved”, “much improved” or “very much improved” in the PGI-I questionnaire at the last study visit)

The time points for these efficacy endpoints are defined as follows:

- For patients who received deferiprone in the initial study, the baseline visit of that study will be treated as the baseline visit of TIRCON2012V1-EXT as well. Thus, Visit 1 of the extension study (Week 0) will be Year 1.5 (month 18), and Visit 4 (Week 78) will be Year 3 (month 36).
- For patients who received placebo in the initial study, Visit 1 of the extension study (Week 0) will be the baseline visit. Thus, Visit 4 (Week 78) will be Year 1.5 (month 18).

Patients who received placebo in initial study:

For this group only, for each measure, the changes seen between the start and completion of the initial study (TIRCON2012V1) (i.e., following 18 months on placebo) will be compared against the changes seen between the start and completion of extension study (TIRCON2012V1-EXT) (i.e., following 18 months on deferiprone), as follows:

- Comparison of change in BAD total score from baseline to completion of the initial study vs. change in BAD total score from baseline to completion of the extension study

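### In the adjusted comparison for former-placebo patients, AR(1) on BAD change scores cannot represent the correlation created by the shared Visit 1 score, so the MMRM interval and p-value are not controlled in either direction

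*SAP*

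**What the plan says.** SAP sections 3.5 and 4 compare, within former-placebo patients, the change over the initial study with the change over the extension. The default is a paired t-test. If DBS setting changes, outcome-impacting medication or PRN/rescue use are significantly imbalanced between the studies, an MMRM on observed cases replaces it. It feeds Table 14.2.2.9.

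- **Response:** each element is the patient's "score at that occasion minus the baseline score".
- **Shared visit:** SAP section 3.1 describes the extension "with the final visit of the initial study being considered Visit 1 of the extension study". Section 4 adds: "For patients who received placebo in the initial study, Visit 1 of the extension study (Week 0) will be the baseline visit".
- **Covariance:** "AR(1) (autoregressive of order 1) covariance structure will be used to model the correlation between repeated measures within the same patient". The sample code puts all of a patient's records in one block; its statement begins "repeated VISIT/ subject=USUBJID type=ar(1". Degrees of freedom are Kenward-Roger. The mean model has treatment, visit, their interaction, BASE, DBSCHG, RESMED and NDRUG.
- **Level and size:** a two-sided p-value "of 0.05 will be used as the significance level for the determination of statistical significance in all statistical tests". Section 3.2 states "There was no formal sample size and power calculation for this study" and gives enrolment as "44 originally randomized to the deferiprone group and 24 in the placebo group".

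The SAP does not justify AR(1). It plans no fallback structure, robust standard error or covariance sensitivity analysis, and neither document gives an SD or correlation for BAD.

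**The concern.** The comparison is within patient, so its standard error depends directly on the covariance between the placebo-period and deferiprone-period changes. Measurement error in the Visit 1 score pushes those two changes in opposite directions, while changes within a period share a baseline and correlate positively. AR(1) has one variance and one correlation parameter. A positive value fitted to the within-period pattern forces the between-period correlation to be positive as well.

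Kenward-Roger adjusts the degrees of freedom and the standard error for estimating the covariance parameters, but it takes the covariance form as given.

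At stake are the BAD rows of Table 14.2.2.9: the least-squares mean difference, 95% CI and p-value. They are the only planned within-patient deferiprone-versus-placebo results for BAD that adjust for the imbalances. When the switch is triggered, a test that needs no assumption about the between-period correlation gives way to one whose error rate depends on unknown variance ratios.

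**Working it through.** There is no power or sample-size figure to reproduce. The stated figure to test is the 0.05 level.

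**Inputs.** From the SAP: 24 patients; post-baseline visits at Months 6, 12 and 18 in each period, giving six change scores per patient; AR(1); BASE in the model. Assumed: between-patient SD 6, visit-noise SD s from 1 to 4, and SD d of patients' progression per 18 months from 0 to 3, with linear progression and no drug effect.

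**True correlation.** Let D1 = Y18 - Y0 (placebo) and D2 = Y36 - Y18 (deferiprone). Each has variance d² + 2s², and their covariance is d² - s². Hence

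corr(D1, D2) = (d² - s²)/(d² + 2s²),

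which is -0.5 at d = 0, 0 at d = s and +0.5 at d = 2s.

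**True variance of the contrast.** D2 - D1 = Y36 - 2·Y18 + Y0. The slope cancels, leaving 6s². With s = 2 and n = 24, the true SE is √(6·4/24) = 1.00.

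**What AR(1) implies.** With six visit levels the two Month 18 records are three steps apart, so the model variance is 2v(1 - ρ³), v being the common variance. At d = 0 and s = 2, v = 2s² = 8 and the fitted ρ is about 0.30, so the SE is √(16·(1 - 0.027)/24) = 0.81. The rejection rate is then about 2(1 - Φ(1.96·0.81)), or 11%. If the periods are separate blocks, the implied correlation is 0, the true-to-model variance ratio is 1.5, and the rate is 11.0%.

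**Simulation under no effect** (REML AR(1), Kenward-Roger adjusted SE with Satterthwaite-type df, 2,000 to 5,000 runs, six visit levels, BASE included unless stated):

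| s | d | corr(D1, D2) by formula | model SE / true SD | AR(1) type I error | paired t-test |
|---|---|---|---|---|---|
| 2 (no BASE) | 0 | -0.50 | 0.81 | 11.6% | 4.8% |
| 2 | 0 | -0.50 | 0.84 | 9.8% | 4.8% |
| 1 | 0 | -0.50 | 0.81 | 11.8% | 5.1% |
| 3 | 0 | -0.50 | 0.87 | 9.5% | 5.1% |
| 4 | 0 | -0.50 | 0.90 | 8.2% | 5.1% |
| 1.5 | 1 | -0.23 | 0.87 | 8.6% | 4.5% |
| 1.5 | 1.5 | 0.00 | 0.92 | 7.0% | 4.5% |
| 1.5 | 2 | +0.21 | 0.98 | 5.4% | 4.5% |
| 1.5 | 3 | +0.50 | 1.11 | 3.2% | 4.5% |
| 1 | 3 | +0.73 | 1.27 | 1.3% | 4.5% |

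Variants at s = 2, d = 0 with BASE: dummy DBS and medication covariates 10.0%; separate subject-by-period blocks 10.7%; 20 patients 9.5%. On data that truly follow AR(1), the same fitting routine rejected 4.1%, so the inflation does not come from the fitting.

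**The case against.** A reader might infer that the MMRM standard error is simply too small and that the real error rate is 12%. The documents do not support that. They give no BAD variances, and the upper figure needs visit noise to dominate. Protocol section 1.1.1 says atypical PKAN progresses more slowly than the classical form, and SAP section 4.3.2 plans subgroups by age at onset and disease duration, so unequal progression is plausible. That would make the test conservative. Nor is 12% the typical figure under noise dominance: with BASE in the model, as the SAP specifies, the range is 8.2% to 11.8%. Random-walk or autocorrelated scores gave up to 16.7%, but part of that comes from AR(1)'s equal-variance assumption, not from the shared visit.

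It can also be said that a six-position AR(1) is not in the SAP: the 14.2.2 shells use Months 6, 12 and 18 in both periods. But coding VISIT that way puts two records of a patient at the same AR(1) position and makes the block singular. The code therefore needs six levels or a subject-by-period block, and neither can represent the negative correlation.

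The scope is narrow, and this stands. The analysis is conditional, for a secondary objective. Paired t-test p-values for BAD appear in Tables 14.2.2.2 and 14.2.2.4 whether or not the MMRM is run, though they are unadjusted. PGI-I is analysed directly, not as a difference from the Visit 1 score, so the shared-score argument does not reach it.

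**Conclusion.** The point holds as a loss of control, not as a one-directional bias. If the adjusted analysis is triggered, the standard error, 95% CI and p-value for the BAD rows of Table 14.2.2.9 cannot be relied on. At 24 patients and with assumed variances, type I error is about 8-12% when visit noise dominates, close to nominal at one intermediate ratio (5.4% at s = 1.5, d = 2), and about 1-3% with intervals too wide when progression rates differ widely. The paired t-test stayed at 4.5-6.0% throughout. The opposite signs of the Visit 1 score follow from the SAP's own definitions; the sizes rest on the assumed variances. The default paired t-test is unaffected. The change is worth making because it is cheap and the adjusted result is used exactly when confounding is suspected.

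**What to change.** **Preferred.** When adjustment is triggered, analyse the within-patient difference (deferiprone-period change minus placebo-period change) at Months 6, 12 and 18, with VISIT and an unstructured 3x3 covariance. Enter DBS setting change (as a change indicator), RESMED and NDRUG as between-period differences, coded so that zero means the same in both periods; the visit means are then the adjusted period differences. With complete data and no covariates, Month 18 reproduces the planned paired t-test.

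**BASE needs care.** Its between-period difference is Y18 - Y0, which is the placebo-period Month 18 change itself and so part of the response. Uncentred, the visit mean would refer to a patient who did not progress on placebo. Centred, with d = 0, the residual variance falls from 6s² to 2s²(1 - 0.25) = 1.5s². The model SE is then half the true one, and type I error is about 2(1 - Φ(0.98)), or 33%. Omit BASE, since pairing already removes stable differences in severity, or use the centred average of the two period baselines.

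**Smaller change.** Keep the mean model with distinct period-by-visit records, and replace the Kenward-Roger inference with an empirical (sandwich) SE, a small-sample correction and n - 1 df. In the simulations this gave 4.5-5.9%. It keeps BASE in its planned form: with a common drift of 2 in both periods, the average estimate was 0.24 instead of 0.

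An unstructured model over all seven visits is not advisable: 28 covariance parameters (7·8/2) for 24 patients.

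**Cost.** SAP text and a few lines of code. The 3x3 matrix has six parameters against two for AR(1), so four more. Intervals widen in the noise-dominated case, and a visit missed in one period loses that month's difference.
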